#### **1.2.4 Clinical safety**

The overall safety experience with nivolumab, as monotherapy or in combination with other therapeutics, is based on experience in approximately 4,000 subjects treated to date. For monotherapy, the safety profile is similar across tumor types. The only exception is pulmonary inflammation adverse events (AEs), which may be numerically greater in subjects with NSCLC, because in some cases, it can be difficult to distinguish between nivolumab-related and unrelated causes of pulmonary symptoms and radiographic changes. There is no pattern in the incidence, severity, or causality of AEs to nivolumab dose level.

In several ongoing clinical trials, the safety of nivolumab in combination with other therapeutics such as ipilimumab, cytotoxic chemotherapy, anti-angiogenics, and targeted therapies is being explored. Most studies are ongoing and, as such, the safety profile of nivolumab combinations continues to evolve. The most advanced combination under development is nivolumab + ipilimumab in subjects with melanoma. Thus far, the combination of both agents results in a safety profile with similar types of AEs as either agent alone, but in some cases with a greater frequency [26].

#### **1.2.5 Biomarkers**

Significant efforts continue to explore potential tumor cells and microenvironment-related biomarkers that could predict response to nivolumab and other checkpoint inhibitors. For instance, tumor cell expression of PD-L1 was characterized with the use of IHC staining and pharmacodynamics changes in the peripheral blood absolute lymphocyte count in the study investigating the combination of nivolumab and

ipilimumab in melanoma [26]. PD-L1 positivity was defined as expression in at least 5% of tumor cells. Among patients treated with the concurrent regimen of nivolumab and ipilimumab, ORs were observed in patients with either PD-L1–positive tumor samples (6 of 13 patients) or PD-L1–negative tumor samples (9 of 22). In the sequenced regimen cohorts, a higher number of overall responses were seen among patients with PD-L1–positive tumor samples (4 of 8 patients) than among patients with PD-L1–negative tumor samples (1 of 13) suggesting the possibility that these tumors have higher response rates to the combination. Other biomarkers such as tissue expression of PDL-2, interferon- $\gamma$  (IFN- $\gamma$ ), IDO (indoleamine-pyrrole 2,3-dioxygenase), and T cell CD8+ infiltration are also being investigated. However, there is no definitive data to support the use of any of these biomarkers to select patients for treatment at this time.

### **1.3 Rationale for the Current Study**

Studies investigating immunotherapy strategies in ACC provide preliminary evidence that anti-tumor immune response can be promoted in this disease. Based on the wide expression of the steroidogenic acute regulatory protein (StAR) in ACC tumors, a specific immune response against this antigen was elicited using an immunization protocol with DNA plasmids and recombinant vaccinia virus vector that resulted in an anti-tumor effect in a xenograft model utilizing tumor cell line expressing StAR [38, 39]. Another study describing vaccination of two patients with metastatic ACC using autologous dendritic cells pulsed with autologous tumor lysate showed tumor-specific immune response in spite of tumor excess production of glucocorticoids [40]. Furthermore, results from molecular studies show that ACC is a heterogeneous disease defined by a wide array of somatic alterations and differential transcriptional patterns. The characteristic genetic instability of ACC with high rate of chromosomal alterations and somatic mutations certainly results in a significant number of neoepitope peptides derived from these altered genes [25]. These neoepitopes can elicit the generation of specific CD4+ T cells capable of killing cancer cells directly [41, 42].

Hence, the proposed association between mutational burden of tumors and clinical benefit from immunotherapy strategies (i.e. checkpoint inhibitors anti-CTLA-4 and anti-PD-1 antibodies), with remarkable anti-tumor effects seen with tumors displaying the highest rates of mutations such as melanoma [43, 44]. This is also illustrated by the anti-tumoral immunologic response to anti-PD-1 antibody in patients with colorectal cancer with increased mutational burden secondary to mismatch repair deficiency [45]. Building upon this scientific rationale supporting the potential for immunotherapies in ACC and the immeasurable clinical need for novel treatments, we propose to investigate the safety and efficacy of nivolumab for the treatment of metastatic ACC. In light of the afore mentioned antitumor activity in solid tumors, well studied pharmacokinetics and toxicity profile a phase II trial is appropriate at this juncture to assess the antitumor activity of nivolumab in these patients at current standard approved dose of 240mg intravenously every 2 weeks.

#### **1.3.1 Rationale for nivolumab dose and schedule**

The dose and schedule of nivolumab in this study will be 240mg every 2 weeks, based upon safety, efficacy, and exposure-response data from ongoing BMS studies. The Phase 1 study, CA209003. Anti-tumor activity was observed in study CA209003 at dose levels ranging from 1 to 10 mg/kg in RCC. The antitumor activity of nivolumab tended to increase with dose, as did the incidence of SAEs. The anti-tumor activity of

nivolumab in RCC was investigated at dose levels 1 and 10 mg/kg, with the higher activity observed at 10 mg/kg. The observed anti-tumor activity in melanoma, and NSCLC was highest at 3 mg/kg, suggesting that anti-tumor activity approaches a plateau at dose levels of 3 mg/kg and above. Consistent with these observations, the results of the exposure-response analyses for these tumor types, show that the probability of a tumor response tended to approach a plateau for trough concentrations produced by 3 and 10 mg/kg every 2 week dosing. Nivolumab was adequately tolerated up to 10 mg/kg, the highest dose level tested, and no maximum tolerated dose (MTD) was identified. Although the spectrum, frequency, and severity of nivolumab-related AEs were generally similar across the dose levels tested, the 10 mg/kg doses level had numerically higher Grade 3/4 drug-related SAEs and AEs leading to discontinuation. Based on the totality of the safety, efficacy, and exposure-response data, a dose of 3 mg/kg every two weeks was selected as the dose anticipated achieving an appropriate balance of benefit and risk.

### 1.3.2 Flat Dose Regimen

The safety and efficacy of 240 mg Q2W flat dose of nivolumab is expected to be similar to 3 mg/kg Q2W dosing regimen. Using the PPK model, exposure of nivolumab at 240 mg flat dose is identical to a dose of 3 mg/kg for subjects weighing 80 kg, which is the approximate median body weight in nivolumab clinical trials. Across the various tumor types in the clinical program, nivolumab has been shown to be safe and well tolerated up to a dose level of 10 mg/kg, and the relationship between nivolumab exposure produced by 3 mg/kg and efficacy and safety has been found to be relatively flat. Given the similarity of nivolumab PK across tumor types and the similar exposures predicted following administration of 240 mg flat dose compared to 3 mg/kg, it is expected that the safety and efficacy profile of 240 mg nivolumab will be similar to that of 3 mg/kg nivolumab. Hence, a flat dose of 240 mg nivolumab is under investigation.

## 1.4 Exploratory Studies

### **To explore the correlation between PD-1, PD-L1 and PD-L2 expression and CD4+ and CD8+ tumor infiltrating lymphocytes and PFS, OS and response to treatment.**

PD-1 is a key immune checkpoint receptor expressed by activated T cells and mediates immunosuppression. PD-1 functions primarily in peripheral tissues, where T cells may encounter the immunosuppressive PD-1 ligands PD-L1 and PDL-2, which are expressed by tumor cells, stromal cells or both [46-48]. PD-L1 and PD-L2 are overexpressed in a variety of solid tumors however no data exists in ACC [46].

There are conflicting data on the predictive value of PD-L1 expression on PD-1 directed therapy in solid tumors [36, 46]. Herbst et al showed that patients with solid tumors including non-small cell lung cancer and melanoma treated with humanized PD-L1 antibody had higher ORR when immunohistochemistry showed intense staining for PD-L1 in the tumor [49]. The same correlation was not observed on stratified analysis according to tumor cell membrane PD-L1

expression of non-small cell lung cancer patients treated with nivolumab therapy in the second line setting [36].

Pathological slides from tumor archival tissue will be stained using a monoclonal antibody against PD-L1 and defined as PD-L1 positive if equal or greater than 5% of the tumor cells membrane analyzed. We hypothesize that tumor cell membrane expression of PD-L1 or PD-L2 can have an impact on treatment responses.

#### **Peripheral blood lymphocyte phenotypes**

Lymphocyte subsets (CD3, CD4, CD8, CD19, and CD56) will be analyzed according to absolute cell numbers per microliter of whole blood, percent representation among all lymphocytes, and coexpression of the activation markers CD25, HLA-DR, and CD45RO using automated flow cytometric techniques at the Flow Cytometry Core Laboratory, Robert H Lurie Cancer Center of Northwestern University under the supervision of [name].

**To measure humoral and cellular responses to tumor antigens on serum samples by measuring the levels of cytokines (ie, IL-2, IL-6, IL-8, IL-10, IL-18, IFN $\gamma$  and TNF- $\alpha$ ) and peripheral blood lymphocyte phenotype.** Measures of immunologic response correlate with lack or presence of response to treatment with nivolumab.

## **2.0 OBJECTIVES & ENDPOINTS**

### **2.1 Primary Objective & Endpoint**

The primary objective will be to assess overall response rate of nivolumab in patients with metastatic or locally advanced adrenocortical carcinoma. Overall response rate will be measured according to RECIST criteria 1.1 at every 8 weeks interval by using CT scans.

### **2.2 Secondary Objectives & Endpoints**

- 2.2.1 To assess the progression free survival defined as time from date of first nivolumab infusion until date of death or evidence of progression of disease as assessed by CT imaging every 8 weeks according to RECIST criteria 1.1.
- 2.2.2 To assess the overall survival defined as time from date of first nivolumab infusion until death of patients with metastatic or locally advanced ACC. The patients will be assessed for survival (either by routine clinic visit or by phone) every 2 weeks while on treatment and every 3 months for up to 2 years after completion of trial to document survival and disease progression,
- 2.2.3 To assess the safety and tolerability profile of nivolumab described by number, frequency, and severity of adverse events according to the National Cancer Institute Common Terminology Criteria for Adverse Events (CTCAE) version 4.0.3 assessed every 2 weeks while patients are on therapy.

### 2.3 Exploratory Objectives & Endpoints

- 2.3.1 To assess the overall response rate, progression free survival and overall survival according to tumor PD-L1 and PD-L2 expression,
- 2.3.2 To assess the overall response rate, progression free survival and overall survival according to serum interleukin levels and peripheral T cell profile levels,
- 2.3.3 To measure humoral and cellular responses to tumor antigens on serum samples by measuring the levels of cytokines (ie, IL-2, IL-6, IL-8, IL-10, IL-18, IFN $\gamma$  and TNF- $\alpha$ ) and peripheral blood lymphocyte phenotype. We will explore potential correlations between differential measures of response and the toxicity and efficacy of nivolumab,

### 3.0 PATIENT ELIGIBILITY

The target population for this study is patients with metastatic or locally advanced ACC who have been treated with mitotane and/or one line of chemotherapy. This will be a multicenter trial conducted at Northwestern University. Northwestern University will serve as the lead site and coordinating center for this study. Participating sites will include Ohio State University, Moffitt Cancer Center, and Johns Hopkins University.

A total of up to 33 subjects will be needed for this trial. Given that this is an NIH rare disease, approximately 5 patients can be enrolled per year. Potential patients may be referred to the Principal Investigator (PI) at Northwestern University, [name] at [contact].

Eligibility will be evaluated by the study team according to the following criteria. Eligibility waivers are not permitted. Subjects must meet all of the inclusion and none of the exclusion criteria to be registered to the study. Study treatment may not begin until a subject is registered.

#### 3.1 Inclusion Criteria

- 3.1.1 Patients must have a histologically confirmed stage IV or unresectable locally advanced adrenocortical carcinoma,
- 3.1.2 Patients must have disease progressing after treatment with at least one line of therapy including mitotane and/or chemotherapy.

Note: Patients who are deemed ineligible to receive first line treatment with mitotane and/or chemotherapy or who decline first line treatment may be eligible for this study after discussion with the PI.

- 3.1.3 Patients must have measurable disease according to the standard RECIST version 1.1. CT scans or MRIs used to assess the measurable disease must have been completed within 28 days prior to registration.
- 3.1.4 Patients must be of age  $\geq 18$  years at the time of study registration.
- 3.1.5 Patients must exhibit an ECOG performance status of 0-3.
- 3.1.6 Patients must have adequate organ and bone marrow functions:
  - leukocytes  $\geq 2,000/\text{mcl}$

- absolute neutrophil count  $\geq 1,500/\text{mcl}$
- hemoglobin  $\geq 9 \text{ g/dL}$
- platelets  $\geq 75,000/\text{mcl}$
- total bilirubin  $\leq 1.5 \times$  institutional upper limit of normal (ULN)  
(except patients with Gilbert Syndrome, who can have total bilirubin  $< 3.0 \text{ mg/dL}$ )
- AST(SGOT)/ALT(SGPT)  $\leq 3 \times$  ULN  
*NOTE: If liver metastases are present, AST/ALT  $\leq 5 \times$  ULN is permitted*
- Serum creatinine of  $< 3.0 \times$  ULN (upper limit of normal) or creatinine clearance  $> 30 \text{ mL/minute}$  (using Cockcroft/Gault formula below):  
Female CrCl =  $\frac{(140 - \text{age in years}) \times \text{weight in kg} \times 0.85}{72 \times \text{serum creatinine in mg/dL}}$   
Male CrCl =  $\frac{(140 - \text{age in years}) \times \text{weight in kg} \times 1.00}{72 \times \text{serum creatinine in mg/dL}}$

3.1.7 Patients with history of central nervous system (CNS) metastases are eligible if CNS disease has been radiographically and neurologically stable for at least 6 weeks prior to study registrations and do not require corticosteroids (of any dose) for symptomatic management

3.1.8 Females of childbearing potential (FOCBP) must have a negative serum or urine pregnancy test (minimum sensitivity 25 IU/L or equivalent units of HCG) within 24 hours prior to the start of study drug.

NOTE: A FOCBP is *any woman* (regardless of sexual orientation, having undergone a tubal ligation, or remaining celibate by choice) who meets the following criteria:

- *Has not* undergone a hysterectomy or bilateral oophorectomy
- *Has had* menses at any time in the preceding 12 consecutive months (and therefore has not been naturally postmenopausal for  $> 12$  months)

3.1.9 FOCBP and men who are sexually active with FOCBP must agree to follow instructions for method(s) of contraception for the duration of treatment and the designated post-treatment period (see Appendix B for details on appropriate contraception methods)

3.1.10 Patients must have the ability to understand and the willingness to sign a written informed consent prior to registration on study

### 3.2 Exclusion Criteria

3.2.1. Patients who have had chemotherapy or radiotherapy within 4 weeks prior to entering the study are not eligible.

3.2.2. Patients who have not recovered to  $\leq$  Grade 1 from adverse events due to agents administered more than 4 weeks earlier are not eligible.

3.2.3. Patients may not be receiving any other investigational agents.

3.2.4. Patients who have a history of allergic reactions attributed to compounds of similar chemical or biologic composition to nivolumab are not eligible.

- 3.2.5. Patients should be excluded if they have had prior treatment with an anti-PD1 or anti-PD-L1. Please contact principal investigator, [name], for specific questions on potential interactions.
- 3.2.6. Patients with active autoimmune disease or history of autoimmune disease that might recur, which may affect vital organ function or require immune suppressive treatment including chronic prolonged systemic corticosteroids (defined as corticosteroid use of duration one month or greater), should be excluded. These include but are not limited to patients with a history of:
- immune related neurologic disease
  - multiple sclerosis
  - autoimmune (demyelinating) neuropathy
  - Guillain-Barre syndrome
  - myasthenia gravis
  - systemic autoimmune disease such as SLE
  - connective tissue diseases
  - scleroderma
  - inflammatory bowel disease (IBD)
  - Crohn's
  - ulcerative colitis
  - patients with a history of toxic epidermal necrolysis (TEN)
  - Stevens-Johnson syndrome
  - anti-phospholipid syndrome

*NOTE: Subjects with vitiligo, type I diabetes mellitus, residual hypothyroidism due to autoimmune condition only requiring hormone replacement, psoriasis not requiring systemic treatment, or conditions not expected to recur in the absence of an external trigger are permitted to enroll.*

- 3.2.7. Patients are ineligible who have any condition requiring systemic treatment with corticosteroids (>10mg daily prednisone equivalents) or other immunosuppressive medications within 14 days prior to first dose of study drug.

*NOTE: Inhaled steroids and adrenal replacement steroid doses >10mg daily prednisone equivalents are permitted in the absence of active autoimmune disease. A brief (less than 3 weeks) course of corticosteroids for prophylaxis (eg, contrast dye allergy) or for treatment of non-autoimmune conditions (eg, delayed-type hypersensitivity reaction caused by a contact allergen) is permitted.*

- 3.2.8. Patients who have an uncontrolled intercurrent illness including, but not limited to any of the following, are not eligible:
- Uncontrolled hypertension – blood pressure  $\geq$  150/90 mmHg despite medical therapy
  - Ongoing or active infection requiring systemic treatment
  - Symptomatic congestive heart failure
  - Unstable angina pectoris
  - Cardiac arrhythmia
  - Psychiatric illness/social situations that would limit compliance with study requirements

- Any other illness or condition that the treating investigator feels would interfere with study compliance or would compromise the patient's safety or study endpoints

3.2.9. Female patients who are pregnant or nursing are not eligible.

3.2.10. No other prior malignancy is allowed except for the following: adequately treated basal cell or squamous cell skin cancer, in situ cervical cancer, adequately treated Stage I or II cancer from which the patient is currently in complete remission, or any other cancer from which the patient has been disease free for at least three years

3.2.11. Known history of testing positive for human immunodeficiency virus (HIV) or known acquired immunodeficiency syndrome (AIDS) is not permitted.

3.2.12. Any known positive test for Hepatitis B or Hepatitis C virus indicating acute or chronic infection is not permitted.

## **4.0 TREATMENT PLAN**

This will be a single-center phase II trial with patients with metastatic or locally advanced ACC who have been treated with at least one line of therapy including mitotane and/or chemotherapy. Patients will be treated with nivolumab 240mg as an intravenous infusion over 30 minutes every 2 weeks until confirmed disease progression, unacceptable toxicity, or withdrawal of consent. Note: Please refer to section 4.2.3 for patients who may continue treatment after initial progression.

### **4.1 Treatment Administration**

Treatment will be administered on an outpatient basis. Reported adverse events and potential risks are described below. No investigational or commercial agents or therapies other than those described below may be administered with the intent to treat the patient's malignancy.

Nivolumab will be administered at a dose of 240mg as an intravenous infusion over 30 minutes every 2 weeks until disease progression, unacceptable toxicity, or withdrawal of consent.

There will be no dose escalations or reductions of nivolumab allowed. Subjects may be dosed no less than 12 days from the previous dose. There are no pre-medications recommended for nivolumab on the first cycle. If an acute infusion reaction is noted, subjects should be managed according to Section 4.2.4.

Nivolumab is to be administered as a 30-minute IV infusion (a window of +/- 5 minutes is allowed), using a volumetric pump with a 0.2/1.2 micron in-line filter at the protocol-specified dose. The drug can be diluted with 0.9% normal saline for delivery but the total drug concentration of the solution cannot be below 1 mg/mL. It is not to be administered as an IV push or bolus injection. At the end of the infusion, flush the line with a sufficient quantity of normal saline.

Subjects will be monitored continuously for AEs while on study. Treatment modifications (e.g., dose delay or discontinuation) will be based on specific laboratory and adverse event criteria.

Early recognition and management may mitigate severe toxicity. Evaluation and Management Guidelines were developed to assist investigators and can be found in the Investigator Brochure:

- Suspected Pulmonary Toxicity
- Diarrhea and Colitis
- Suspected Hepatotoxicity (including asymptomatic liver function tests [LFT] elevations)
- Suspected Endocrinopathy
- Nephrotoxicity

#### **4.2 Dosing delays, support care, and discontinuation of therapy**

There will be no dose modifications allowed for management of toxicities.

Nivolumab administration should be delayed for the following until resolution to  $\leq$  Grade 1:

- Any Grade  $\geq 2$  non-skin, drug-related adverse event, with the following exceptions:
  - Grade 2 drug-related fatigue or laboratory abnormalities do not require a treatment delay
  - Any Grade 3 skin, drug-related adverse event
  - Any Grade 3 drug-related laboratory abnormality, with the following exceptions for lymphopenia, leukopenia, AST, ALT, or total bilirubin:
    - Grade 3 lymphopenia or leukopenia does not require dose delay
    - If a subject has a baseline AST, ALT or total bilirubin that is within normal limits, delay dosing for drug-related Grade  $\geq 2$  toxicity
    - If a subject has baseline AST, ALT, or total bilirubin within the Grade 1 toxicity range, delay dosing for drug-related Grade  $\geq 3$  toxicity
- Any adverse event, laboratory abnormality, or intercurrent illness which, in the judgment of the investigator, warrants delaying the dose of study medication.

Immuno-oncology (I-O) agents are associated with AEs that can differ in severity and duration than AEs caused by other therapeutic classes. Nivolumab is considered an immuno-oncology agent in this protocol. Early recognition and management of AEs associated with immuno oncology agents may mitigate severe toxicity. Management Algorithms have been developed to assist investigators in assessing and managing the following groups of AEs:

- Gastrointestinal
- Renal
- Pulmonary
- Hepatic
- Endocrinopathy
- Skin
- Neurological

The above algorithms are found in the nivolumab Investigator Brochure and appendix D of this protocol.

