##### **4.2.1 Treatment discontinuation criteria**

Nivolumab treatment should be permanently discontinued for the following:

- Any Grade 2 drug-related uveitis, eye pain or blurred vision that does not respond to topical therapy and does not improve to Grade 1 severity
- Any Grade 3 non-skin, drug-related adverse event lasting > 7 days
- Grade 3 drug-related uveitis, pneumonitis, bronchospasm, hypersensitivity reaction, or infusion reaction of any duration requires discontinuation
- Grade 3 drug-related laboratory abnormalities do not require treatment discontinuation except:
  - Grade 3 drug-related thrombocytopenia > 7 days or associated with bleeding requires discontinuation
  - Any drug-related liver function test (LFT) abnormality that meets the following criteria requires discontinuation:
    - AST or ALT > 5-10x ULN for > 2 weeks
    - AST or ALT > 10x ULN
    - Total bilirubin > 5x ULN
    - Concurrent AST or ALT > 3x ULN and total bilirubin > 2x ULN
- Any Grade 4 drug-related adverse event or laboratory abnormality, except for the following events:
  - Grade 4 neutropenia  $\leq$  7 days does not require discontinuation
  - Grade 4 lymphopenia or leukopenia does not require discontinuation
  - Isolated Grade 4 electrolyte imbalances/abnormalities that are not associated with clinical sequelae and are corrected with supplementation/appropriate management within 72 hours of their onset do not require discontinuation
  - Isolated Grade 4 amylase or lipase abnormalities not associated with symptoms or clinical manifestations of pancreatitis. The PI and Data Monitoring Committee (DMC) should be notified of Grade 4 amylase or lipase abnormalities (please do so by sending an email to [[contact]](mailto:[contact]))
- Any dosing interruption lasting > 6 weeks with the following exceptions:
  - Dosing interruptions to manage drug-related adverse events, such as prolonged steroid tapers, are allowed. Prior to re-initiating treatment in a subject with a dosing interruption lasting > 6 weeks, the PI and DMC should be consulted (by emailing [[contact]](mailto:[contact])). Tumor assessments should continue as per protocol even if dosing is interrupted.

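### For patients enrolled with AST/ALT above the Grade 1 range, the restart rule in 4.2 read literally requires a value better than the baseline accepted in 3.1.6

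*Combined protocol and SAP*

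**What the plan says.** **Entry.** Section 3.1.6 limits AST/ALT to 3x ULN. A note relaxes this: "If liver metastases are present, AST/ALT" may be as high as 5x ULN.

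**Delay trigger.** Section 4.2 lists as a reason to delay "Any Grade 3 drug-related laboratory abnormality, with the following exceptions for lymphopenia, leukopenia, AST, ALT, or total bilirubin". For the liver tests it then gives two baseline-specific rules:
- Normal baseline: "If a subject has a baseline AST, ALT or total bilirubin that is within normal limits, delay dosing for drug-related Grade" 2 or higher.
- Grade 1 baseline: "If a subject has baseline AST, ALT, or total bilirubin within the Grade 1 toxicity range, delay dosing for drug-related Grade" 3 or higher.

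No rule names a baseline above Grade 1. The same list states "Grade 2 drug-related fatigue or laboratory abnormalities do not require a treatment delay", and it ends with an item that leaves other delays to the investigator's judgment.

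**Restart.** One lead-in governs the whole list: "Nivolumab administration should be delayed for the following until resolution to" Grade 1 or lower.

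**Long holds.** Section 4.2.1 makes this a reason for permanent discontinuation: "Any dosing interruption lasting > 6 weeks with the following exceptions". The first exception allows interruptions to manage drug-related adverse events, with PI and DMC consultation before dosing restarts.

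**Algorithms.** Section 4.2 refers to the hepatic algorithm in Appendix D and the Investigator Brochure. Only the introductory text and footnotes of that algorithm are readable here. They deal with delay versus discontinuation and with steroid use, not with restart.

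**The concern.** The eligibility limit and the dosing rules do not describe the same patients. Someone enrolled at, say, 4x ULN because of liver metastases is acceptable for a first dose. If the drug raises AST/ALT, dosing is held, and the value then returns to 4x ULN, the patient is back in the state in which the protocol enrolled them. The restart condition is still not met.

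Section 3.0 names four institutions, and they could reasonably differ. One may hold until the value falls below baseline. Another may treat a return to baseline as resolution. Section 11.5 requires the study to be run exactly as written outside emergencies, so the second site risks a recorded deviation. Safety and tolerability is a secondary objective (2.2.3). In this subgroup, the length of holds, the exposure and the reasons for stopping would then depend partly on how a site reads 4.2.

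**Working it through.** The plan states no figure on this point, so there is nothing to reproduce. The check compares the entry limit with the restart limit.

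**Inputs**
- Upper entry limit for AST/ALT with liver metastases: 5x ULN (3.1.6).
- Restart target: Grade 1 or lower (4.2).
- Grading scale: CTCAE 4.0.3 (7.2 and Appendix A). The documents do not print its AST/ALT limits. Let G be the upper limit of Grade 1, assumed to be 3x ULN and varied below.
- Discontinuation limits (4.2.1): AST/ALT above 5 to 10x ULN for more than 2 weeks; AST/ALT above 10x ULN; total bilirubin above 5x ULN; AST/ALT above 3x ULN together with bilirubin above 2x ULN.

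**Step 1. Does a gap exist without the unprinted limits?** Section 4.2.1 places the range above 5 to 10x ULN under its item on Grade 3 laboratory abnormalities. If Grade 3 starts just above 5x ULN, Grade 2 lies below that and Grade 1 must end below 5x ULN. This is an implication rather than a definition, because the same sub-list also holds the combined criterion that starts at 3x ULN. On this reading, some patients whom 3.1.6 admits start above Grade 1, whatever the exact value of G.

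**Step 2. Who is affected?** Baselines B with G < B ≤ 5x ULN. With G = 3, that is above 3x and up to 5x ULN.

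**Step 3. How far below baseline must the value be?** Required fall = 1 − G/B.

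| Baseline B (x ULN) | G = 2.5 | G = 3 (assumed) | G = 4 |
|---|---|---|---|
| 4 | 1 − 2.5/4 = 37.5% | 1 − 3/4 = 25% | not affected |
| 4.8 | 1 − 2.5/4.8 = 47.9% | 1 − 3/4.8 = 37.5% | 1 − 4/4.8 = 16.7% |
| 5 | 1 − 2.5/5 = 50% | 1 − 3/5 = 40% | 1 − 4/5 = 20% |

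The gap closes only if Grade 1 reaches 5x ULN.

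**Step 4. Can a patient get there without meeting 4.2.1?** Take a baseline of 4.8x ULN and a drug-related rise to 5.5x ULN that returns to 4.8x ULN within a week, with bilirubin never above 2x ULN. The peak is under 10x ULN. The time above 5x ULN is under 2 weeks, and the combined criterion is not met. A week also stays within the 7-day limit in 4.2.1 for Grade 3 non-skin events, should a site apply that item to laboratory values. Discontinuation is not required, yet with G = 3 the restart condition fails at 4.8x ULN.

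**Step 5. Does other text change the restart target?**
- The 6-week exceptions extend the hold. They set no new threshold.
- The investigator-judgment item in 4.2 adds a reason to delay. It does not permit restart above Grade 1.
- Exclusion 3.2.2 concerns recovery from adverse events of earlier agents, not enzyme elevation from liver metastases.
- The readable Appendix D text has no restart criterion. The chart itself could not be checked.

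**The case against.** The strongest reply is that the hold is for a drug-related abnormality. Once AST/ALT is back at a level explained by the metastases, the drug-related event has resolved and dosing may restart. A site could reasonably read 4.2 that way. But 4.2 defines resolution by a grade, and the liver limits in 4.2.1 are multiples of ULN rather than of baseline. If recovery to baseline is meant, the text does not say so.

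A second reply is that the hepatic chart may settle the matter. That cannot be excluded. If the chart does allow restart at baseline, 4.2 says something different and the two still need aligning.

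Several stronger readings are tempting, and the documents do not support them:
- **That 4.2 has no rule at all for these patients.** The two baseline rules are exceptions within a general Grade 3 laboratory item. A patient fitting neither could fall back on that item or on investigator judgment. The trigger is unclear, not missing.
- **That all patients with liver metastases are affected.** Only those with a baseline above Grade 1 are, and only when AST/ALT itself caused the hold. A hold for another event ends when that event resolves.
- **That the 6-week rule would force these patients off treatment.** The exception for drug-related events covers this situation, so that consequence largely disappears.
- **That the same gap exists for bilirubin in Gilbert syndrome.** Section 3.1.6 gives that limit in mg/dL. The documents give neither a bilirubin ULN in those units nor the bilirubin grade limits, so the claim cannot be tested.

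**Conclusion.** The passages conflict as written, within a narrow group: patients with liver metastases, enrolled with AST/ALT above the Grade 1 limit, held for a drug-related AST/ALT rise that meets no 4.2.1 criterion, and returning to a value still above Grade 1. For them the literal restart rule demands a result better than baseline: 25% lower at 4x ULN and 40% lower at 5x ULN, if Grade 1 ends at 3x ULN. The percentages rest on that assumption. The existence of the gap needs only a Grade 1 limit below 5x ULN, which 4.2.1 implies. The conclusion is also conditional on the unread hepatic chart.

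The severity is minor. The documents do not let one estimate how many of the up to 33 patients would be affected. A reader might infer that the primary result is at risk, but the documents do not support this. A patient is evaluable for response after one dose and a re-evaluation (6.2.1), tumor assessments continue through dosing interruptions (4.2.1, 6.1), and adverse events are summarized descriptively (10.2). Sample size and error rates are unaffected.

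As context only, Appendix E records that Amendment 2 added the 5x ULN allowance, while its entry for 4.2 mentions only the added algorithms. That history is not itself an error.

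**What to change.** Reconcile 3.1.6, 4.2, 4.2.1 and the Appendix D hepatic algorithm so that together they give one delay trigger and one restart criterion for patients enrolled with AST/ALT above the Grade 1 range. State the AST/ALT grade limits in x ULN, or refer to them explicitly, so that sites apply the same boundaries. The clinical team chooses the rule; this review proposes no threshold and no change to eligibility.

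The cost is a short wording amendment and a note to sites. It adds no procedures or patients and changes nothing in section 10.
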